10.2.2 Reactogenicity (for Vaccine Studies and Some Therapeutic Trials)

Reactogenicity events are referred to as solicited adverse events. Refer to Section 10.1 for a list of solicited adverse events (systemic and injection site reactions) and timing of collection. Diary cards will be provided to participants for recording of solicited systemic adverse events (for 7 days) and solicited injection site reactions (for 28 days; see Section 9.1 for further details regarding diary cards).

10.2.3 Serious Adverse Events

Definition of Serious Adverse Event

Seriousness refers to the outcome of an adverse event. Seriousness is determined by both the investigator and the local medical monitor. If the investigator or local medical monitor determines an event to be serious, it will be classified as such. If any of the following outcomes are present, then the adverse event is serious:

- It results in **death** (i.e., the AE caused or led to the fatality). Serious does not describe an event which hypothetically might have caused death if it were more severe.
- It was immediately **life-threatening** (i.e., the AE placed the participant at immediate risk of dying. It does not refer to an event which hypothetically may have led to death if it were more severe).
- It required inpatient hospitalization or prolonged hospitalization beyond the expected length of stay. Hospitalizations for scheduled treatments and elective medical/surgical procedures related to a pre-existing condition that did not increase in severity or frequency following receipt of investigational product, are not serious by this criterion. Hospitalization is defined as a hospital admission or an emergency room visit for a period greater than 24 hours.

 It resulted in a persistent or significant disability/incapacity (i.e., substantial reduction of the participant's ability to carry out activities of daily living).

Other medically important conditions that may not result in death, threaten life or require hospitalization (i.e., the AE does not meet any of the above serious criteria) may be considered a serious adverse event when, based on appropriate medical judgment, they may jeopardize the participant and require medical or surgical intervention to prevent one of the serious outcomes listed in these criteria (e.g., allergic bronchospasm requiring intensive treatment in an emergency room or at home; blood dyscrasias or convulsions that do not result in hospitalization).

A serious adverse event is an adverse event meeting the outcome criteria for seriousness regardless of relationship to an administered medicinal product. Recording and follow up of serious adverse events is discussed in Section 10.4.

Definition of Suspected Unexpected Serious Adverse Reaction (SUSAR)

When an adverse event is judged to be related to an investigational product, is judged to be serious and unexpected, and is in a participant who received active vaccine, it is a SUSAR (suspected unexpected serious adverse reaction) and is subject to expedited reporting.

10.2.4 Procedures to be Followed in the Event of Abnormal Laboratory Test Values or Abnormal Clinical Findings

Results from clinical assessments and laboratory tests obtained on the study must be reviewed by the investigator, and the participant managed in accordance with the clinical trial site policies. The clinical significance of any change in a vital sign or laboratory parameter will be determined by the investigator and may be reported as an adverse event at the discretion of the investigator (using the toxicity tables in Appendix B, C and D to grade severity). Additional laboratory tests may be performed if the investigator deems them to be necessary to fully evaluate an adverse event. In the event that the investigator elects to order non-protocol-specified laboratory tests, the investigator must record the rationale for the tests and a determination of clinical significance of the result in the source documents. The investigator must keep the medical monitor informed of vaccine-related adverse events of clinical significance.

Abnormal results and findings will be discussed as applicable with the participant, and the participant will be referred for follow-up with their healthcare provider if necessary.

10.3 Reporting Procedures

The reporting period for all adverse events is specified in Section 10.1. Reporting procedures for adverse events are described in Section 10.2.1.

10.3.1 Serious Adverse Events

Serious adverse events, which include SUSARs, will be reported by the PI to the sponsor, local medical monitor, UCT HREC and TCD in an expedited fashion. TCD RA in turn will notify SAHPRA according to their required timelines. SUSARs are reported even after the trial is over, if the principal investigator/investigator or local medical monitor becomes aware of them.

Serious adverse events will be assessed by the investigator and the local medical monitor according to their roles for severity, causal relationship to the study vaccine, and expectedness. The onset and resolution dates of the event and the action taken in response to the event will be documented. If the event has not resolved by the final study visit, it will be documented as "ongoing" on the eCRF. However, follow-up of the SAE must continue until resolved. Information recorded on the eCRF must be substantiated in the source documents.

SAEs are to be reported to the sponsor within 24 hours of the investigator site becoming aware of the event, even if all information concerning the event is not yet known at that time. SAHPRA stipulates that a SUSAR is to be reported to SAHPRA within 7 calendar days if it is fatal or life threatening, and within 15 calendar days if the SUSAR is not fatal or not life threatening. Other SAEs should be submitted as part of 6 monthly reports to SAHPRA in a line-listing format.

The UCT HREC are to be notified as soon as possible but not later than 7 days of all SAE's, SSAR's and SUSAR's. New information which may impact the conduct of a study should be reported to HREC within 3 days.

Follow-up reports for the SAE are to be provided by the site as new information becomes available or when the status of the SAE changes.

Fatal or life-threatening serious adverse events that the investigator suspects are related to the vaccination should be telephoned to the local medical monitor immediately upon the investigator's awareness of the event. If the local medical monitor or PI is required by the protocol or chooses to suspend enrollment s/he shall immediately create a written memorandum for record to the study file and immediately notify the sponsor, UCT HREC and SAHPRA of this act.

Contact information for all safety personnel are contained in the Team Contact List which will be stored on site in the Site Regulatory Binder and maintained by the PI.

The sponsor will notify the DSMB and the manufacturers of MTBVAC and BCG of all SUSARs within 3 working days of becoming aware of an event and will provide all follow-up information in a timely manner.

Investigators must not wait to collect additional information to fully document the event before notifying the local medical monitor/research monitor of a serious adverse event. The initial notification should include the following (at minimum):

- Protocol number and name and contact number of the investigator
- Participant ID number (and initials and date of birth, if available)

- Date participant received investigational product
- Serious adverse event(s) and date of event onset
- Current status of participant

10.3.2 Suspected and Confirmed Tuberculosis Events

Any adverse event suspected to be or confirmed as tuberculosis disease will be assessed, documented and reported according to the same procedures as for serious adverse events (refer to section 10.3.1), even if the event does not meet any of the serious adverse event criteria as per section 10.2.3. Such suspected or confirmed tuberculosis disease events will be classified as Immediately Reportable Events (IREs). These events will be assessed by the investigator and the local medical monitor according to their roles for severity, causal relationship to the study vaccine, and expectedness. The onset and resolution dates of the event and the action taken in response to the event will be documented. If the event has not resolved by the final study visit, it will be documented as "ongoing" on the eCRF. However, follow-up of the IRE must continue until resolved. Information recorded on the eCRF must be substantiated in the source documents.

10.3.3 Other Immediately Reportable Events

The investigator must report the following events to the sponsor within 24 hours of becoming aware of the event:

- Withdrawal of consent during the study for safety reasons
- Emergency unblinding (see Section 10.6)
- Protocol violation affecting the safety of a participant or involving the vaccination process
- Adverse event thought to be an allergic reaction to the investigational product
- Any event that, in the opinion of the investigator, precludes further administration of the investigational product

10.4 Type and Duration of Follow-up of Participants after Adverse Events

The duration of follow up for AEs is described in Section 10.1.

Treatment of any adverse events will be determined by the investigator using his/her best medical judgment and according to current clinical practice guidelines. All applied measures as well as follow-up will be recorded in the appropriate eCRF.

Adverse events will be considered resolved when the condition returns to normal or returns to the participant's baseline status as established on Study Day 0, or when the condition has stabilized with the expectation that it will remain chronic.

The investigator will continue follow-up on adverse events, including laboratory abnormalities and solicited adverse events, until the event has resolved, is otherwise satisfactorily explained, or the participant completes the study. The resolution date will be recorded on the eCRF as the last date on which the participant experienced the adverse event. If an adverse event resolution date is uncertain the investigator should estimate the completion date based on medical judgment and interview of the participant. Approximate dates of resolution from interviews may be taken as adverse event resolution dates. Some examples of estimation of adverse event resolution are: 1) an asymptomatic laboratory abnormality on one visit that has not been followed-up between visits but has resolved by the next visit may be assumed to have resolved by the midpoint of the inter-visit interval; 2) A resolved adverse event that was treated may be assumed to have been resolved by the end of treatment. Adverse events that are still present at the end of the trial should be recorded as ongoing. Information recorded on the eCRF must be substantiated in the source documents. If an adverse event evolves into a condition that becomes "serious," it will be designated as serious on the AE eCRF and a Supplemental SAE Report (SAER) form will be completed.

Follow-up for serious adverse events must continue until resolution and the outcome reported to the sponsor, even if this extends beyond the serious adverse event reporting period (i.e., after the final study visit). For analysis purposes, the outcome for serious adverse events will be determined on the final study visit.

Outcome of all adverse events will be classified as one of the following:

- Resolved
- Resolved with sequelae
- Ongoing
- Death

If at any time after completion of the serious adverse event reporting period (the final study visit) the investigator becomes aware of a serious adverse event that is suspected by the investigator to be related to the investigational product, the event must be reported to the sponsor.

10.5 Pausing Rules

These rules govern the pausing and stopping of investigational product administration at any time during the study such as between individuals within a single cohort, and between cohorts. Enrolment to study will be paused if certain pre-defined conditions are met. Follow-up of study participants and pre-enrolment recruitment may continue while a study pause is in effect. The trial can be paused independently by either the PI, or the local medical monitor. Written notification via fax or e-mail of the study pause must be made to the PI, local medical monitor,

UCT HREC, sponsor, DSMB and SAHPRA within 24 hours of its effect and a memorandum recorded in the study site file.

If the principal investigator pauses study vaccine administration in a trial under the rules in this section and additional clinical information becomes available that reduces the principal investigator's assessment of causality, severity or toxicity grade such that the adverse event's causality, severity or toxicity grade no longer requires pausing then the principal investigator, with the agreement of the local medical monitor, may resume study vaccine administration with a memorandum to the study regulatory binder. In such a case a formal study pause need not be affected.

In all cases where the study has been paused, the DSMB will be convened, except in the case where the PI revises his assessment of a study pause condition before the meeting is convened, as additional information becomes available to him, to review safety reports and any other pertinent data following the study pause. Additional information, results of investigations, or unblinded data may show that potential risks to participants are lower, or less generalized, than suspected. If, after meeting and deliberating on all relevant information, the DSMB determines that it is safe for the study to continue, the study pause may be lifted, and enrolment and vaccination may continue. Restrictions may be placed, if appropriate, on further study conduct, additional safety or monitoring measures may be put in place, or recruitment and vaccination may be stopped completely if participant safety cannot be quaranteed. The sponsor, PI, LMM, UCT HREC and SAHPRA will be notified in writing via fax or email of the decisions and recommendations, and a signed memorandum of the deliberations will be provided to the sponsor, UCT HREC, SAHPRA, and will also be kept in the site regulatory binder. Any changes to the protocol required as a condition of study enrolment resumption must be approved by, the Institutional Review Board/Ethics Committee (UCT HREC) and SAHPRA.

The following rules will trigger pausing by the principal investigator, local medical monitor, or the sponsor of further screening, enrollment, and investigational product administration, and DSMB review of safety data:

- Severe (e.g., painful, draining, infected [abscess]) or large (e.g., >10.00 cm induration and erythema, and >3.0 cm ulceration) injection site reaction, excluding local injection site reactions that decrease to <Grade 3 within 24 hours.
- 2. Large (≥5 cm) local regional lymphadenopathy or suppurative lymphadenitis. *OR*
- 3. One or more SAE(s) judged related to investigational product occurs. *OR*
- 4. Anaphylaxis or bronchospasm within 4 hours of injection, indicative of an immediate hypersensitivity reaction to the study injection.
- 5. Two or more participants in any given cohort experience a Grade 3 or higher event, excluding local injection site reactions, judged related to investigational product. *OR*
- 6. An adverse event pattern of concern occurred.

If the principal investigator, local medical monitor or sponsor pauses the study, the decision will be recorded in a memorandum to the study file and will trigger DSMB review. If a recommendation to resume study enrollment and investigational product administration is made, the DSMB will record their judgment in a memorandum to the study file and notify the sponsor. The DSMB memorandum will be forwarded to the medical monitors and principal investigator. The DSMB may recommend resumption of enrollment with changes to the protocol if it judges that such changes will reduce safety risks. However, the final decision to resume study activities, amend the protocol, or terminate the study will be made by the sponsor. The clinical trial site will be allowed to resume activities only upon receipt of written notification from the sponsor. Decisions regarding pausing and resumption of the study will be communicated promptly to the IRB/IEC by the principal investigator and to the applicable national regulatory authority by the sponsor (or designee).

In addition, the study may be discontinued at any time by the applicable national regulatory authority, the IRB/IEC, the sponsor, or other governmental agencies as part of their duties to ensure that research participants are protected.

10.6 Emergency unblinding

If the PI is of the opinion that unblinding of a particular participant's randomization result is essential to treat an adverse event and that the participant's safety would be compromised without this information, the PI may unblind the randomization result for a specific participant. In such cases, the PI should, if at all possible, consult the local medical monitor first for concurrence. If emergency unblinding has occurred, a memorandum will be filed in the site regulatory binder detailing the occurrence.

The DSMB must, if possible, immediately be informed of any unblinding.

10.7 Safety Oversight (DSMB)

The DSMB, composed of a panel of independent experts, will operate according to its charter. If investigational product administration is paused for safety reasons by the local medical monitor or the principal investigator, the DSMB will be convened. Based on its review and the protocol pause rules (Section 10.5) the DSMB will make recommendations to the sponsor regarding further conduct of the study and further administration of investigational product. The DSMB may review an individual SAE or it may choose to review adverse events, serious adverse events, solicited adverse events, and laboratory and vital signs data. The DSMB may unblind any amount of safety information needed to conduct their assessment. All procedures associated with this review, including objectives, data handling, and elements to be included for review will be documented in DSMB minutes. The DSMB may recommend suspension or resumption of enrollment and investigational product administration after review of safety data. However, the sponsor will make the final decision to suspend or resume study activities. The recommendations of the DSMB, along with the sponsor's decision, will be communicated to the investigators, IRB/IEC, and the national regulatory authorities or the IRB/IEC.

The DSMB will conduct three planned safety data reviews during dose-escalation, as described in Section 12.3.1. Two planned safety data reviews will solely focus on safety, with a third safety data review including the review of immunogenicity data together with safety data to confirm the safest and most immunogenic dose of MTBVAC, as described in Section 12.3.1 and 12.3.2.

10.8 Trial Steering Committee (TSC)

The Sponsor will establish a Trial Steering Committee (TSC) before the start of the clinical trial. The TSC will, based on a TSC charter, supervise clinical trial conduct as well as consider the advice from the DSMB. An independent expert member will chair the TSC that will furthermore be composed of 2 additional independent expert members. A representative of EDCTP will participate as an observer. The TSC will monitor trial progress and conduct and provide advice on scientific credibility. The TSC will consider the recommendations of the DSMB and will provide additional advice to the Sponsor as to whether a trial needs to be stopped, suspended, or resumed on scientific grounds and/or efficacy. However, the sponsor will make the final decision to stop, suspend or resume study activities. The TSC will meet annually in person and via Skype on a regular basis, or ad hoc when required. The TSC will reach advice by consensus and will minute meetings.

Any resolution leading to a protocol amendment, pausing rules or as per safety consideration, will be communicated to the regulatory authorities and Ethics Committee. This is in addition to the regular 6-monthly Study progress reports.

A European Ethics Committee, "Comité Autonómico de Ética da Investigación de Galicia" (Sergas), will be involved in the study as ethical advisor. This Committee will be informed from the beginning and throughout the study on Study Progress Reports, any Protocol amendment as well as any Safety Event that may occur.

11 CLINICAL MONITORING

11.1 Site Monitoring Plan

The study will be monitored regularly, according to the protocol-specific monitoring plan, by the sponsor or its designee throughout the study period. Monitoring will be a combination of on-site monitoring and central review of data in the electronic database. One hundred percent (100%) of data will be reviewed centrally and in-house review of data will be done on an ongoing basis with formal review meetings approximately monthly. On-site monitoring will occur approximately monthly during recruitment and vaccination periods and approximately every 2 months during follow up. On-site monitoring will include source data verification of approximately 80% of study data.

12 STATISTICAL CONSIDERATIONS

12.1 Study Hypotheses

No formal hypothesis testing will be performed, since the trial is not powered to do any formal testing (see sample size section below).

12.2 Sample Size Considerations

The sample size for this study was selected as being adequate for a preliminary assessment of the safety profile of MTBVAC in neonates, rather than for statistical reasons. The sample sizes of Phase 1 and 2a clinical trials are conventionally not powered to detect rare or infrequent events, but rather common safety events, major safety signals, or important trends. The sample size of 99 infants was selected as adequate for such initial evaluation of the safety profile of MTBVAC, rather than for statistical reasons (17-25).

12.3 Planned Interim Analyses

12.3.1 Safety Review

Pausing rules are described in Section 10.5. The DSMB (see Section 10.7) will conduct two safety data reviews during dose-escalation, at the following time points:

- Participants in Cohort 2 have completed the Study Day 28 visit.
- Participants in Cohort 3 have completed the Study Day 28 visit.

Dose-escalation will proceed as described in Section 5, as long as no pausing rules are triggered.

In addition to dose-escalation DSMB safety data reviews, an additional safety data review will take place at the following time point:

Participants in Cohort 3 have completed the Study Day 182 visit.

Dose selection of MTBVAC for the Phase III study will proceed based on the results of the analysis of all of the safety data available for all cohorts up to the time that Cohort 3 Study D182 visit has been completed.

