- Record any adverse events, including unsolicited adverse events, solicited and unsolicited injection site reactions, and serious adverse events (including concomitant medications).
- 8. Examine site of injection (includes measurement of redness, swelling, and ulceration) and take a pus swab if discharge present.
- 9. Blood collection for:
 - Immunogenicity WB-ICS
 - QuantiFERON®-TB Gold Plus test

Study Day 120 ±7 days and Study Day 270 ±7 days

Home / telephonic visit if infant tested QFT positive at D56 to enquire about TB signs and symptoms and general well-being

Study Day 182

Allowable window for clinic visit is 182 ±14 days from Study Day 0 visit date.

- 1. Verbally reconfirm consent.
- 2. Update medical history including use of medications.
- 3. Screening for potential new TB exposure and TB symptoms.
- 4. Record feeding practice.
- 5. Vital signs (heart rate, respiratory rate, axillary temperature, weight and recumbent length).
- 6. Focused physical examination.
- 7. Record any adverse events, including unsolicited adverse events and serious adverse events (including concomitant medications).
- 8. Examine site of injection (includes measurement of redness, swelling, and ulceration) and take a pus swab if discharge present.
- 9. Blood collection for:
 - Immunogenicity WB-ICS
 - QuantiFERON®-TB Gold Plus

Partial Cohort Unblinding of Data Post Study Day 182

Once the last Cohort 3 Study D182 visit has been completed, an independent biostatistician be unblinded to available study data. At this point Cohort 1 and Cohort 2 participants will have completed all study visits and these participants and clinical team will be unblinded post Study D365 visit. All available safety data for all cohorts up to the last Cohort 3 Study D182 visit completion; and immunogenicity data for all cohorts up to each cohort's Study D182 visit, will be analysed by the independent, unblinded biostatistician and provided to DSMB for review to determine MTBVAC dose selection for the Phase III study. The Sponsor will review blinded data only in order to keep the blind until post Study D365 visit. The DSMB will be provided with the same blinded data along with unblinding vaccine recipient lists. The DSMB review will allow for a blinded recommendation and input into the dose selection for the Phase III study. For all cohorts, unblinding of the clinical team and participants will take place post Study D365 visit.

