10.1 Specification of Safety Parameters

Safety parameters that constitute the primary outcome measures of the study are described in Section 4.2.1. The time periods for collection of adverse events are as follows.

Unsolicited Adverse Events

Unsolicited adverse events will be collected from informed consent until trial completion.

Solicited Adverse Events

Solicited systemic adverse events will be collected post-vaccination through the Study Day 28 visit (with diary cards to be used for 7 days after vaccination).

Solicited injection site reactions will be collected post-vaccination through the Study Day 56 visit (with diary cards to be used for 28 days after vaccination).

Solicited adverse events are events the participant is specifically asked about. These adverse events are commonly observed soon after receipt of vaccines. For this study, solicited adverse events to be collected include:

- Solicited systemic adverse events:
 - fever, irritability, vomiting, diarrhea, drowsiness, poor feeding, skin rash.
- Solicited injection site reaction adverse events:
 - pain, redness, swelling, ulceration, drainage, and regional lymphadenopathy.

Solicited adverse events of injection site reactions will be considered causally related to investigational product.

All participants' caregivers will be provided a diary card to record axillary temperature and information regarding occurrences of these specific events for the first 7 days (for systemic adverse events) or 28 days (for injection site reaction adverse events) of the solicited adverse event reporting period.

Serious Adverse Events

Serious adverse events will be collected throughout the entire study period (i.e., 365 days post-vaccination).

Site of Injection Examination

Site of injection examinations will be performed at the visits noted in the schedule of events in Appendix A. The following will be assessed at each examination:

• Tenderness/pain, redness, swelling, warmth, ulceration, presence of infection/abscess, crusting, drainage, scarring, and regional lymphadenopathy.

Any of the above-mentioned injection site reactions that meet adverse event criteria according to the Toxicity Table in Appendix C will be recorded as adverse events.

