12.4.4 Safety Analyses

12.4.4.1 Adverse Events

The primary endpoint is the frequency of adverse events (AEs) by MTBVAC dose compared to BCG. In order to assess the primary endpoint, analysis of the data will be preceded by a

blinded data review meeting in order to address population determination and miscellaneous data queries pertinent to analysis of the primary endpoint.

Safety and reactogenicity data will be evaluated by study arm and cohort in all participants in the safety analysis set. The primary variable for evaluation of safety will be the frequency of unsolicited, solicited adverse events and injection site reactions at all available post-vaccination time points. The number and percentage of participants with adverse events will be summarized by MedDRA system organ class (SOC) and preferred term (PT), as well as by severity and relationship to study vaccine. Informal between-group comparisons will be performed using the Chi-square or Fisher Exact test. The Cochran-Mantel-Haenzel test will be used to compare the effect of dose on reactogenicity (injection site adverse events).

Separate listings will be provided for participants with serious adverse events. SAEs may also be summarized by MedDRA system organ class and preferred term.

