16.5 Timing/Reports

Line lists of all adverse events will be reported to the sponsor, UCT HREC, DSMB, SAHPRA and local medical monitor, on a 6-monthly basis or per the guidelines or SOPs of each of these bodies. Serious adverse events will be reported to the sponsor within 24 hours of detection, to UCT HREC and SAHPRA as per their respective guidelines.

Data will be reviewed on a regular basis throughout the trial. DSMB reviews of safety data will be conducted at specified time points during dose-escalation, and on an ad hoc basis if the study is paused for safety reasons (see Section 10.7 for further details of DSMB reviews). A DSMB review on safety and immunogenicity data will be conducted after completion of the last Cohort 3 Study D182 visit. This safety and immunogenicity review will assist in dose selection for the Phase III study and will include all available safety data for all cohorts up to the last Cohort 3 Study D182 visit, as well as all immunogenicity data up to Study D182 visit per each cohort.

Coding (medical history, concomitant medications, and adverse events) will occur on an ongoing basis throughout the study, including prior to DSMB reviews. A final coding review and approval will be carried out prior to database lock.

The blind will be maintained throughout the trial, unless there is a need to unblind a participant for safety reasons (see Section 10.6) or unblinding is requested by the DSMB (see Section 10.7). Unblinding of an independent biostatistician only is planned once the last Cohort 3 Study D182 visit has been completed in preparation for a safety and immunogenicity review (see Sections 8.3 and 12.3.2). Unblinding of the data for preparation of the final study report is planned when the database has been locked, which will occur after all data (with the exception of data relating to the immunology and exploratory objectives) have been entered, reviewed, and all queries related to the data have been addressed.

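### The D182 dose-selection review uses up to twice the follow-up in Cohorts 1 and 2 as in Cohort 3 for unsolicited AEs, SAEs and TB events, with no common window stated

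*Combined protocol and SAP*

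**What the plan says.** Three places set the safety data for the dose-selection review by one calendar date. Section 12.3.1 times the review at "Participants in Cohort 3 have completed the Study Day 182 visit" and uses "analysis of all of the safety data available for all cohorts up to the time that Cohort 3 Study D182 visit has been completed". Section 8.3 (partial unblinding after D182) gives the same rule, "All available safety data for all cohorts up to the last Cohort 3 Study D182 visit completion", and Section 16.5 repeats it. Section 8.3 also says of the lower cohorts: "At this point Cohort 1 and Cohort 2 participants will have completed all study visits".

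Immunogenicity is handled differently. Section 16.5 describes the review as covering the safety data "as well as all immunogenicity data up to Study D182 visit per each cohort", so immune responses are compared at a matched time in every cohort.

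Section 10.1 sets the collection windows. Solicited systemic events are collected through D28 and solicited injection site reactions through D56. For the rest, "Unsolicited adverse events will be collected from informed consent until trial completion", and SAEs are collected for 365 days.

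The only safety summary described is the number and percentage of participants with events, by study arm and cohort (Section 12.4.4.1, within the final analysis plan). No person-time rate and no common window for safety appears in the document. Section 10.7 says the third DSMB review is meant to confirm the safest and most immunogenic dose.

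**The concern.** If the top dose is given, each dose level sits in its own cohort, and the cohorts are enrolled one after another. A single calendar cut then gives the earlier, lower-dose cohorts more time in which an unsolicited AE, SAE or TB event can be counted. A crude percentage of infants affected rises with time at risk. Equal true risk would therefore show as fewer affected infants in Cohort 3, and a true excess at the top dose could be hidden. The comparison with pooled BCG has the same fault, because 16 of the 24 BCG infants belong to Cohorts 1 and 2.

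The stake is the dose carried forward. Section 3.2 describes going straight from this trial to Phase III with a single selected dose, so this review has unusual weight for a descriptive look at 25 infants per dose.

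**Working it through.** The plan states no event rate, exposure or power figure for this review, so there is nothing to reproduce. The check is follow-up arithmetic.

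**Inputs from the protocol.** Cohorts 1 and 2 complete to D365 at the cut (8.3). Cohort 3 has at least 182 days (12.3.1). Each cohort has 25 MTBVAC and 8 BCG infants (Section 5 and Figure 5-1). **Assumptions.** The same constant hazard in every arm; 10% or 20% risk of a given event type per 182 days; uniform accrual within Cohort 3.

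**1. Exposure ratio at the floor.** 365/182 = 2.01.

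**2. Cohort 3 mean follow-up.** 182 days applies to the last infant enrolled; earlier infants have more. If the last Cohort 2 infant has reached D365 when the last Cohort 3 infant reaches D182, their enrolments are at least 365 - 182 = 183 days apart. With a gap of g days before Cohort 3 opens, its accrual lasts at least 183 - g days and the mean is 182 + (183 - g)/2:
- g = 28 (assumed): 182 + 155/2 = 259.5 days, ratio 365/259.5 = 1.4
- g = 120 (assumed): 182 + 63/2 = 213.5 days, ratio 365/213.5 = 1.7

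A 90-day accrual gives 182 + 45 = 227 days. The next scheduled visit after D182 is D365, so follow-up actually captured in Cohort 3 lies between 182 days and these means. Accrual longer than the minimum would raise them.

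**3. Apparent risk.** Risk by day t = 1 - (1 - p)^(t/182). At day 365 this is 1 - 0.9^2.01 = 19.0% for p = 10%, and 1 - 0.8^2.01 = 36.1% for p = 20%. The chance that Cohort 3 shows fewer affected infants than Cohort 1 comes from exact binomials, 25 against 25, treating every Cohort 3 infant as followed for the stated time:

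| Cohort 3 follow-up | Cohort 3 v Cohort 1, p = 10% | Cohort 3 fewer | Cohort 3 v Cohort 1, p = 20% | Cohort 3 fewer |
|---|---|---|---|---|
| 182 days (floor) | 10.0% v 19.0% | 76% | 20.0% v 36.1% | 87% |
| 227 days | 12.3% v 19.0% | 68% | 24.3% v 36.1% | 78% |
| 260 days | 14.0% v 19.0% | 62% | 27.3% v 36.1% | 70% |
| Equal windows (both 182) | 10.0% v 10.0% | 40% | 20.0% v 20.0% | 43% |

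The last row is the benchmark. It falls below 50% because ties are counted separately. At the floor Cohort 3 shows more affected infants in only 13% (p = 10%) and 7% (p = 20%) of trials. A true hazard 2.0 times higher in Cohort 3 would look equal at the floor; at 260 days the factor is 365/260 = 1.4.

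**4. Pooled BCG.** (16 x 19.0% + 8 x 10.0%)/24 = 16.0%, and (16 x 36.1% + 8 x 20.0%)/24 = 30.7%, against 10.0% and 20.0% in Cohort 3 at the floor. Mean BCG follow-up is (16 x 365 + 8 x 182)/24 = 304 days.

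**5. Early clustering.** If a share f of the year's events occurs by D56 and the rest evenly to D365, D182 captures f + (1 - f) x 126/309. For f = 40%, 60% and 80% that is 65%, 76% and 88%. With 76% to 88% captured by D182, the chance that Cohort 3 shows fewer falls to about 60% to 51% where Cohort 1 stands at 19.0%, and about 70% to 57% where it stands at 36.1%.

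**6. A rate from the protocol.** Section 3.3.1 cites 13% unconfirmed TB over 2 years in an earlier infant trial in the same community. That is 1 - 0.87^0.5 = 6.7% at one year and 3.4% at 182 days: 1.68 against 0.85 expected infants of 25. Cohort 3 would show fewer in about 58% of trials, against 38% with both followed to D365.

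**7. Default allocation.** If the top dose is not opened, Cohort 3 adds 13 infants to 2.5 x 10^5 and 12 to 2.5 x 10^4. Mean follow-up pooled by dose is then (25 x 365 + 13 x 182)/38 = 302 days and (25 x 365 + 12 x 182)/37 = 306 days, beside 304 for BCG. The imbalance between doses all but disappears.

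**The case against.** A reader might infer that the top dose is bound to look safer overall. The documents do not support that. Every solicited event is complete in all cohorts at the cut, and solicited events make up two of the three safety items in Section 4.2.1. The planned Cochran-Mantel-Haenszel dose comparison concerns injection site events, and solicited reactions are complete by then. The wording about the top dose is also conditional, as step 7 shows.

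A reader might also say that dose and follow-up are wholly inseparable. That goes too far: Cohort 3 randomises 8 concurrent BCG infants, and Section 12.4.4.1 evaluates safety by arm and cohort. This comparison is balanced, but 8 infants give little information and it does not align one dose with another.

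The best counter-argument is that the plan does not prescribe a biased interim table. The number-and-percentage summary belongs to the final analysis, when all cohorts have reached D365 and no imbalance arises. The DSMB works under a charter not included here, receives recipient lists, may unblind what it needs, and could compare equal windows because onset dates are recorded. There is no formal testing, and the pausing rules do not rest on between-dose percentages. All of that stands. It does not remove the point, because the unequal data cut is a stated rule for this review, the plan nowhere asks for equal windows, and the detailed analysis plan is due only before database lock, with no requirement that it precede the D182 review.

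**Conclusion.** The concern holds for unsolicited AEs, SAEs and TB events, and only for crude comparisons between doses or against pooled BCG. Follow-up in Cohorts 1 and 2 is up to 2.0 times that in Cohort 3, and about 1.4 to 1.7 times under the assumed accrual (Cohort 3 mean 214 to 260 days). If Cohort 3 receives 2.5 x 10^6 CFU, the direction always favours that dose. The 76% to 87% figures are the floor case. They rest on constant hazard and assumed risks of 10% to 20% per 182 days, and should be read against 40% to 43%, not against zero. Longer Cohort 3 follow-up and early clustering both shrink the effect.

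This should be fixed before the D182 review, since afterwards the dose has been chosen. It does not undermine the reactogenicity comparison, the final D365 analysis or the within-cohort comparison with BCG.

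**What to change.** In Sections 8.3, 12.3.1 and 16.5, state that between-dose and dose-versus-BCG comparisons of unsolicited AEs, SAEs and TB events for dose selection use events with onset up to each participant's own D182 visit, matching the immunogenicity cut. Rates per person-time are an acceptable alternative. State also that the DSMB receives all later events in every cohort as a supplementary listing, so that no safety data are withheld.

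The cost is a sentence in each section, one extra filter in the DSMB tables, and fewer events in the main comparison.
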